3.1. Randomization

Refer to Protocol Amendment 3 dated 01 DEC 2021 for a full description of randomization.

3.2. Control of Type I Error

Refer to Protocol Amendment 3 dated 01 DEC 2021 for a full description of control of Type I error.

3.3. Sample Size Considerations

Refer to Protocol Amendment 3 dated 01 DEC 2021 for a full description of the sample size considerations.

3.4. Schedule of Assessments

Refer to Protocol Amendment 3 dated 01 DEC 2021 for a full description of all study procedures and assessment schedules for this study.

4. DATA HANDLING DEFINITIONS AND CONVENTIONS

The term "study drug" refers to INCB001158 only, and "study treatment" refers to INCB001158, daratumumab SC, or the combination of INCB001158 and daratumumab SC.

4.1. Scheduled Study Evaluations and Study Periods

4.1.1. Day 1

Day 1 is the date that the first dose of study treatment (INCB001158 or daratumumab SC) is administered to the participants.

4.1.2. Study Day

If a visit/reporting date is on or after Day 1, then the study day at the visit/reporting date will be calculated as

$$\text{Day \#} = (\text{visit/reporting date} - \text{Day 1 date} + 1).$$

If the visit/reporting date is before Day 1, then the study day at the visit/reporting date will be calculated as

$$\text{Day \#} = (\text{visit/reporting date} - \text{Day 1 date}).$$

A study day of -1 indicates 1 day before Day 1.

4.1.3. Baseline Value

Baseline is the last nonmissing measurement obtained before the first administration of study treatment (INCB001158 or daratumumab SC), unless otherwise defined.

When scheduled assessments and unscheduled assessments occur on the same day and the time of the assessment or time of first dose is not available, use the following convention to determine baseline:

- If both a scheduled and an unscheduled visit are available on the day of the first dose and the time is missing, use the scheduled assessment as baseline.
- If all scheduled assessments are missing on the day of the first dose and an unscheduled assessment is available, use the unscheduled assessment as baseline.

4.1.4. Handling of Missing and Incomplete Dates

In general, values for missing dates will not be imputed unless methods for handling missing dates are specified in this section or relevant sections. The original reported dates collected on the eCRF should be used in all relevant listings. The following rules will be used for handling partial dates for analyses requiring dates.

A partial disease diagnosis date will be handled as follows in calculations:

- If only the day is missing, then the first day of the month will be used.
- If both the month and day are missing, then 01 JAN of the year will be used.
- If the diagnosis date is completely missing, then no imputation will be done.

A missing or partial date of the last dose will be handled as follows:

- If only the day is missing, then the earlier date of the last day of the month or the date that the participant discontinued treatment will be used.
- If both the month and day are missing, then the earlier date of 31 DEC of the year or the date that the participant discontinued treatment will be used.
- Otherwise, the date that the participant discontinued treatment will be used as the date of the last dose.

For relevant efficacy endpoints, a partial date of the death date will be handled as follows in the calculation:

- If mm/yyyy for the last known alive date = mm/yyyy for the death date, then the death date will be set to the day after the last known alive date.
- If mm/yyyy for the last known alive date < mm/yyyy for the death date, then the death date will be set to the first day of the death month.
- Otherwise, the partial death date will not be imputed.

4.1.5. Cycle Length and Duration

Cycle 1 Day 1 is the day that the first dose of study treatment is administered. The scheduled cycle length is 28 days. INCB001158 will be administered on a continuous dose schedule.

Daratumumab SC administration will be once weekly for Cycles 1 and 2, once every 2 weeks for Cycles 3 to 6, and once every 4 weeks thereafter.

The estimated duration of study participation contains up to 28 days for screening, continuous treatment in consecutive 28-day cycles as long as participants are receiving benefit and have not met any criteria for study withdrawal, and every 8 to 12 weeks for follow-up.

4.2. Variable Definitions

The following variables will only be calculated if not reported on the eCRF.

4.2.1. Prior and Concomitant Medication

Prior medication is defined as any nonstudy medication started before the first dose of INCB001158 or daratumumab SC.

Concomitant medication is defined as any nonstudy medication that is started accordingly:

- Before the date of first administration of INCB001158 or daratumumab SC and is ongoing throughout the study or ends on/after the date of first study drug administration.
- On/after the date of first administration of INCB001158 or daratumumab SC and is ongoing or ends during the course of study.

A prior medication could also be classified as "both prior and concomitant medication" if the end date is on or after first dose of INCB001158 or daratumumab SC. In the listing, it will be indicated whether a medication is only prior, only concomitant, or both prior and concomitant.

For the purposes of analysis, all medications will be considered concomitant medications unless the medications can unequivocally be defined as not concomitant.

Additional rules that will be applied for the analysis and classification of prior and concomitant medications are given below:

- Consider the following cases as prior medication.
 - The end date is before the first dose date.
 - If the day of end date is missing, and the last day of the month is before the first dose date.
 - If the month of end date is missing, and the last day of the year is before the first dose date.
- Consider the following cases as concomitant medication.
 - The start date is after the first dose date.
 - If the day of start date is missing, and the first day of the month is on or after the first dose date.
 - If the month of start date is missing, and the first day of the year is on or after the first dose date.
- All other cases will be considered as both prior and concomitant medication.

5. STATISTICAL METHODOLOGY

5.1. General Methodology

Unless otherwise noted, SAS® software (SAS Institute Inc, Cary, NC; v9 or later) will be used for the generation of all tables, graphs, and statistical analyses. Descriptive summaries for continuous variables will include but not be limited to the number of observations, mean, standard deviation, median, minimum, and maximum. Descriptive summaries for categorical variables will include the number and percentage of participants in each category.

Interim analyses are planned for this study as defined in Section 9.

5.2. Study Phases and Treatment Groups

All summaries will be presented by dose level for Phase 1 and by treatment group for Phase 2. Note that separate listings will be provided for Phase 1 and Phase 2.

5.2.1. Phase 1: Dose Escalation

In Phase 1, INCB001158 (50-100 mg PO BID) in combination with daratumumab SC will be administrated in 28-day treatment cycles.

5.2.2. Phase 2: Expansion

Participants will be randomized 1:1:1 to Treatment Groups A, B, or C as follows:

- Treatment Group A: INCB001158 + daratumumab SC
- Treatment Group B: daratumumab SC monotherapy (Part 1), then crossover to INCB001158 + daratumumab SC (Part 2)
- Treatment Group C: INCB001158 monotherapy (Part 1), then crossover to INCB001158 + daratumumab SC (Part 2)

Treatments will be administrated in 28-day cycles for Treatment Groups A, B, and C.

5.3. Analysis Populations

5.3.1. Enrolled

This population will include all participants who sign the ICF.

5.3.2. Full Analysis Set

The FAS will include all participants who received at least 1 dose of INCB001158 or daratumumab SC. Participants will be analyzed according to the treatment to which they have been initially assigned.

This population will be used for summaries of demographics, baseline characteristics, participant disposition, safety, and exposure.

5.3.3. DLT Evaluable Population for Phase 1

The DLT evaluable population includes participants who have received at least 42 of 56 doses for the 28-day cycle regimen (representing $\geq 75\%$ of the dose planned) of INCB001158 or who have a DLT.

Note that the DLT evaluable population will exclude participants in the randomized part (Phase 2) of the study.

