2.2. Study Objectives and Endpoints

[Table 1](#) presents the objectives and endpoints.

Due to early termination decision following recruitment challenge (no safety-related concerns), primary safety analyses but no efficacy analyses will be performed due to insufficient number of participant enrolled in Phase 2.

Table 1: Objectives and Endpoints

Objectives	Endpoints
Primary	
Phase 1: To determine the safety, tolerability, and RP2D of INCB001158 in combination with daratumumab SC.	Safety and tolerability determined by monitoring the frequency, duration, and severity of AEs.
Phase 2: To compare the ORR of the RP2D of INCB001158 in combination with daratumumab SC to daratumumab SC monotherapy.	ORR, defined as the proportion of participants with a documented response PR or better, as per IMWG criteria.
Secondary	
Phase 1: To determine the efficacy of INCB001158 in combination with daratumumab SC.	ORR, defined as the proportion of participants with a documented response PR or better, as per IMWG criteria.
Phase 2: To determine the safety and tolerability of INCB001158 monotherapy at RP2D, and to compare the safety and tolerability and RP2D of INCB001158 in combination with daratumumab SC to daratumumab SC monotherapy	Safety and tolerability determined by monitoring the frequency, duration, and severity of AEs.
Phase 1: To determine the efficacy of INCB001158 in combination with daratumumab SC. Phase 2: To estimate the efficacy of INCB001158 monotherapy, and to compare the efficacy of INCB001158 in combination with daratumumab SC to daratumumab SC monotherapy.	
• TTR, defined as the time from the first dose of study drug to the first documented response PR or better, as per IMWG criteria.• DOR, defined as time from first documented response PR or better, as per IMWG criteria, until date of disease progression or death, whichever occurs first.• PFS, defined as the duration from the date of first dose of study drug until either PD, as per IMWG criteria, or death, whichever occurs first.• MRD, defined as the percentage of MRD-negative participants.• OS, defined as the time from the first dose of study drug to death from any cause.

Table 1: Objectives and Endpoints (Continued)

Objectives	Endpoints

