8.2.4. Adverse Event Summaries

An overall summary of AEs by dose level for Phase 1 and by treatment group for Phase 2 using the FAS population as applicable will include the following:

- Number (%) of participants reporting any TEAEs
- Number (%) of participants reporting any serious TEAEs
- Number (%) of participants reporting any Grade 3 or higher TEAEs
- Number (%) of participants who had a fatal TEAE
- Number (%) of participants who had a TEAE related to INCB001158
- Number (%) of participants who had a TEAE related to daratumumab SC
- Number (%) of participants who had a TEAE related to INCB001158 and/or daratumumab SC
- Number (%) of participants who had a Grade 3 or higher TEAE related to INCB001158
- Number (%) of participants who had a Grade 3 or higher TEAE related to daratumumab SC
- Number (%) of participants who had a Grade 3 or higher TEAE related to INCB001158 and/or daratumumab SC
- Number (%) of participants who had a serious TEAE related to INCB001158
- Number (%) of participants who had a serious TEAE related to daratumumab SC
- Number (%) of participants who had a serious TEAE related to INCB001158 and/or daratumumab SC

- Number (%) of participants who had a TEAE leading to temporary interruption of INCB001158
- Number (%) of participants who had a TEAE leading to INCB001158 dose reduction
- Number (%) of participants who had a TEAE leading to permanent discontinuation of INCB001158
- Number (%) of participants who had an irAE

The following summaries will be produced by MedDRA term for the Phase 1 and Phase 2 FAS population (if 10 or fewer participants appear in a table, a listing may be appropriate):

- Summary of TEAEs by SOC and PT
- Summary of TEAEs by PT in decreasing order of frequency
- Summary of Grade 3 or higher TEAEs by PT in decreasing order of frequency
- Summary of serious TEAEs by PT in decreasing order of frequency
- Summary of INCB001158 treatment-related TEAEs by PT in decreasing order of frequency
- Summary of Grade 3 or higher INCB001158 treatment-related TEAEs by PT in decreasing order of frequency
- Summary of TEAEs with a fatal outcome by SOC and PT
- Summary of TEAEs leading to INCB001158 dose reduction by PT in decreasing order of frequency
- Summary of TEAEs leading to INCB001158 dose interruption by PT in decreasing order of frequency
- Summary of TEAEs leading to discontinuation of INCB001158 by PT in decreasing order of frequency

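### Phase 2 safety is tabulated by initial assignment with no split at crossover in Groups B and C, and the TEAE start is worded so that daratumumab monotherapy falls outside it

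*SAP*

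**What the plan says.** SAP 5.3.2 sets the rule for the FAS: "Participants will be analyzed according to the treatment to which they have been initially assigned". It then gives the uses of that set: "This population will be used for summaries of demographics, baseline characteristics, participant disposition, safety, and exposure". SAP 5.2 fixes the layout: "All summaries will be presented by dose level for Phase 1 and by treatment group for Phase 2". SAP 6 repeats this, and SAP 8.2.4 plans "An overall summary of AEs by dose level for Phase 1 and by treatment group for Phase 2 using the FAS population as applicable".

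SAP 5.2.2 defines Group B as daratumumab SC alone followed by crossover to the combination, and Group C as INCB001158 alone followed by the same crossover. Protocol 4.1.2 and Table 12 place the crossover at confirmed progression.

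SAP 2.2 retains the secondary Phase 2 objective of determining the safety of INCB001158 monotherapy and "to compare the safety and tolerability and RP2D of INCB001158 in combination with daratumumab SC to daratumumab SC monotherapy". The SAP drops the efficacy analyses, so safety is what it still tabulates.

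On timing, SAP 4.1.5 states "Cycle 1 Day 1 is the day that the first dose of study treatment is administered", and SAP 4.1.3 takes one baseline before the first dose of either agent unless otherwise defined. SAP 8.2.1 and protocol 10.4.2.1 start the TEAE period at the first dose of study drug; SAP 4 and protocol 6.1 reserve that term for INCB001158.

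**The concern.** A participant in Group B or C can contribute two periods on different regimens, but the plan gives one column per group. An event that starts on the combination after progression would be counted under a group that opened as monotherapy. The same holds for laboratory, vital-sign and ECG values. A reader using the Group B or C column as the monotherapy profile, as the retained objective invites, would be reading a mixture.

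The protocol does not ask for this. Section 4.1.2 states the as-randomised rule for efficacy, and Table 27 uses the FAS for demographics, baseline characteristics and disposition. The SAP extends the as-assigned FAS to safety and exposure, and SAP 10.1 does not record the extension.

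The TEAE wording is a second problem, confined to Group B. That group takes no INCB001158 in Part 1, so a TEAE period that opens with INCB001158 opens only at crossover, or never.

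**Working it through.** **1. Is there a split anywhere?** Parts 1 and 2 appear in the SAP only in the group definitions (5.2.2). The sections on exposure (6.4), adverse events (8.2), laboratory tests (8.3), vital signs (8.4) and ECGs (8.5) set no crossover cut-off. No Appendix A title names a part or crossover, and listings are split by phase only. The shells are in a separate document that was not available.

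**2. Which displays would mix the two periods?** Group B has no INCB001158 in Part 1, and Group C has no daratumumab in Part 1. With the TEAE start read as either agent:

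| Display | Group B | Group C |
|---|---|---|
| All-cause AE tables (3.2.2-3.2.4, 3.2.7, all-cause lines of 3.2.1) | Mixed | Mixed |
| INCB001158-specific AE tables (3.2.5, 3.2.6, 3.2.8-3.2.10) | Essentially Part 2 only | Mixed |
| INCB001158 exposure | Part 2 only | Mixed |
| Daratumumab exposure | Mixed | Part 2 only |
| Laboratory, vital signs, ECG | Mixed | Mixed |

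The word 'essentially' allows for missing causality, which SAP 8.2.1 counts as related. The exposure rows apply only if exposure is shown by group. SAP 6.4 refers to the combined Phase 1 and Phase 2 FAS, while SAP 5.2 and 6 say by dose level and treatment group.

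**3. Cycle labels.** Protocol Table 12 restarts Part 2 at Cycles 1 and 2, and protocol Tables 4 and 6 give Part 2 its own Cycle 1 Day 1. SAP 4.1.5 has a single Cycle 1 Day 1. The SAP has no rule for a second Cycle 1 in the daratumumab dose-per-cycle summary (6.4.2) or in the by-visit summaries (8.3 to 8.5).

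**4. TEAE start.** The SAP 8.2.1 text combined with the SAP 4 definition gives the first INCB001158 dose. In Groups A and C that agent belongs to the first treatment, so nothing is lost. In Group B every Part 1 event precedes it. SAP 8.2.1 treats an event as a TEAE unless it is unequivocally not one, but that default does not cover an event clearly dated before INCB001158. So on the literal wording the Group B TEAE columns hold Part 2 events only, and on the likely intended wording they hold both parts. Neither isolates monotherapy.

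**5. Illustration of pooling in Group B.** The documents state no pooled figure to reproduce. Inputs:
- p = 30/156 = 19.2%, the Grade 4 or higher AE rate on daratumumab alone (protocol 10.5.2.2).
- q = 40%, the combination rate in that section's stopping-rule scenario. It is not an expected rate.
- c, the fraction crossing over. This is assumed, because the documents do not give it.

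Part 1 events are counted, that is, with the TEAE wording corrected. With independent periods and crossover unrelated to Part 1 events, pooled rate = 1 - (1 - p)(1 - cq). With no assumption on dependence, the range is max(p, cq) to p + cq.

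| c | Independent periods | No assumption |
|---|---|---|
| 0 | 19.2% | 19.2% |
| 0.25 | 1 - 0.808 × 0.90 = 27.3% | 19.2-29.2% |
| 0.50 | 1 - 0.808 × 0.80 = 35.4% | 20.0-39.2% |
| 0.75 | 1 - 0.808 × 0.70 = 43.4% | 30.0-49.2% |
| 1.00 | 1 - 0.808 × 0.60 = 51.5% | 40.0-59.2% |

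If the Part 2 rate were also 19.2%, the pooled rate under independence would be 1 - 0.808 × 0.904 = 27.0% at c = 0.50 and 1 - 0.808 × 0.808 = 34.7% at c = 1. Part of the rise is therefore added observation time and not a different regimen.

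In a group of 10 (the planned equal-randomisation size) with 5 crossing over and q = 40%, the expected number with an event is 10 × 0.192 = 1.9 in Part 1 and 10 × 0.354 = 3.5 pooled (range 2.0 to 3.9).

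**The case against.** **The gap is inferred from silence.** Appendix A gives titles and not column layouts, and the shells or the sponsor's standard safety tables could already split by part. Protocol Tables 3 to 6 give each part its own schedule, and SAP 3.4 refers to the protocol for schedules. This stands as a reason for moderate confidence. It does not supply an analysis rule, and SAP 5.3.2 points the other way.

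**The mixing is narrower than it looks.** A reader might infer that every Group B and C display, including exposure, is contaminated. The documents do not support that. Five of the ten AE tables are specific to INCB001158, so in Group B they are essentially Part 2 only. By-agent exposure is already Part 2 only for INCB001158 in B and daratumumab in C, and SAP 6.4 leaves open whether exposure is shown by group at all.

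**The TEAE wording is loose usage.** SAP 4.1.1, 4.1.3 and 5.3.2 refer to either agent, the protocol abbreviation list says study treatment, Listing 2.5.3 applies the term study drug to daratumumab, and SAP 8.2.4 counts TEAEs related to daratumumab SC. A reader might infer that the sponsor means to exclude monotherapy events; these passages indicate otherwise. The text still needs correcting, because a programmer could apply it as written.

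**The practical effect is small.** No test or decision rule uses the B or C column, Phase 2 closed with few participants, tables may become listings (SAP 8.1, 8.2.4), and the AE and dosing listings let a reader place events by date. All of this stands and sets the grade.

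**Conclusion.** Wrong as written, but minor, with moderate confidence. If anyone crossed over, the plan puts post-crossover safety data in the column of a group that began on monotherapy, so that column does not serve the retained objective. The fault lies in the all-cause AE tables and the laboratory, vital-sign and ECG summaries of both groups, and in the INCB001158-specific AE tables of Group C. For exposure it is limited to daratumumab in B and INCB001158 in C, subject to resolving SAP 6.4. The TEAE start is a probable wording error that affects Group B only; no size is put on it.

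The percentages should not be read as an estimate of bias in this trial. They use a grade threshold that the SAP does not tabulate (it uses Grade 3 or higher), a stopping-rule scenario, an assumed crossover fraction and a planned group size. Without an assumption on dependence, the inflation can be zero at 25% crossover and 0.8 points at 50%. If nobody crossed over, pooling has no effect.

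**What to change.** - **SAP 8.2.1:** define TEAEs from the first dose of study treatment (either agent).
- **SAP 5.3.2, 8.2 to 8.5 and Appendix A:** report Groups B and C by part. End Part 1 the day before the first Part 2 dose and assign each AE to the part in which it starts. A worsening, which SAP 8.2.1 collects as a separate AE, goes to the part in which it occurs. If few participants crossed over, use listings flagged by part instead of extra columns.
- **SAP 4.1.5:** label Part 2 cycles and visits separately, so that the repeated Cycle 1 does not collide with the first in per-cycle and by-visit summaries.
- **SAP 6.4:** reconcile the combined-FAS wording with SAP 5.2 and 6, and split by part where exposure is shown by group.
- **SAP 10.1:** record these changes. If the shells already separate the parts, say so in the SAP text.

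A new Part 2 baseline is optional. It isolates change on the combination but hides change accumulated since entry.

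The cost is SAP wording plus extra columns or a flag, built from dates on the two dosing eCRFs. The drawbacks are smaller denominators, shorter Part 1 follow-up than the pooled column, and sparse Part 2 data after Amendment 3, when safety collection narrows to SAEs, AESIs and pregnancy and laboratory results need not be entered in the eCRF.
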